#### 11.6 The Hospital Anxiety and Depression Scale

The HADS is a PRO, comprises 7 questions for anxiety and 7 questions for depression, with each answer being graded from 0 to 3 with a higher score indicating a worse condition. For each group of questions, scores of 7 or less indicate cases without anxiety or depression, whereas scores of 8 to 10, 11 to 14, and 15 to 21 indicate mild, moderate, and severe cases, respectively. The HADS is one of the tools recommended by the National Institute for Health and Care Excellence for diagnosis of depression and anxiety.

Any patient with a score for depressive symptoms  $\geq 15$  at baseline will not be eligible for enrollment in the study. Patients with a clinically significant worsening of depressive symptoms or new occurrence of clinically significant depression during the study may be referred to a mental health specialist (psychiatrist or clinical psychologist) for further evaluation. After a mental health specialist evaluation, the final decision on restarting or permanently discontinuing study treatment will be at the discretion of the Investigator in consultation with the mental health specialist. These cases should be reported as an AESI. Refer to Section 11.8.2.

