#### 11.7 The Columbia-Suicide Severity Rating Scale

The C-SSRS, Investigator-administered version, was designed to provide a prospective, standardized measure of suicidality. The scale allows clinicians and researchers alike to assess the severity and lethality of suicidal behaviors and ideations and can be used to monitor treatment outcomes and establish suicide risk in a variety of research and clinical settings. Requiring approximately 5 minutes for completion, the C-SSRS is administered in the form of a clinical interview.

This C-SSRS is available in 2 versions: 1 for use at screening referring to the past year and 1 for use throughout the rest of the study referring to the time since the prior visit.

If at screening or baseline there are "yes" answers on item 4 or 5, the patient will not be included in the study.

Any patient with a positive response at subsequent visits (answers "yes" to questions 1-5) should be referred to a mental health specialist (psychiatrist or clinical psychologist) for further evaluation, and the study medication should be paused. After a mental health specialist evaluation, the final decision on restarting or permanently discontinuing study treatment will be at the discretion of the Investigator in consultation with the mental health specialist. These cases should be reported as an AESI. Refer to Section 11.8.2.

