All AEs must be graded by using the National Cancer Institute Common Terminology Criteria for Adverse Events (CTCAE) grading system version 5.0 (CTCAE- Version 5.0) with reference to the unique clinical descriptions of severity for each AE in the guidance document. Please see Table 6 for selected unique clinical descriptions of severity of AEs. Only if an AE is not uniquely described in the CTCAE grading system, the general guidance for classification is to be used. Please see Table 7 for the general guideline for classification.

If a patient experiences a TEAE assessed as Grade 3 or higher using the unique clinical descriptions of severity (Grade 2 or higher for the SOC of cardiac disorders) according to CTCAE version 5, the patient should be permanently discontinued from the study drug and not receive additional doses.

Specific guidelines for classifying AEs by intensity are given in Table 6 and Table 7 and relationship to study drug are given in Table 8.

CTCAE Term	Grade 1	Grade 2	Grade 3	Grade 4	Grade 5
Diarrhea	Increase of <4 stools per day over baseline; mild increase in ostomy output compared to baseline	Increase of 4 - 6 stools per day over baseline; moderate increase in ostomy output compared to baseline; limiting instrumental ADL	Increase of >=7 stools per day over baseline; hospitalization indicated; severe increase in ostomy output compared to baseline; limiting self care ADL	Life-threatening consequences; urgent intervention indicated	Death
Nausea	Loss of appetite without alteration in eating habits	Oral intake decreased without significant weight loss, dehydration or malnutrition	Inadequate oral caloric or fluid intake; tube feeding, TPN, or hospitalization indicated	-	-
Vomiting	Intervention not indicated	Outpatient IV hydration; medical intervention indicated	Tube feeding, TPN, or hospitalization indicated	Life-threatening consequences	Death

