# **11.8.2** Adverse Events of Special Interest (AESI)

An AESI (serious or nonserious) is one of scientific and medical concern, for which ongoing monitoring and rapid communication by the Investigator to the Sponsor could be appropriate. AESIs must be reported within 24 hours of occurrence or when the Investigator becomes aware of the event, following SAE reporting procedures (Section 11.8.4). Such an event might require further investigation to characterize and understand it. Depending on the nature of the event, rapid communication by the trial Sponsor to other parties (eg, regulators) might also be warranted.

In this trial, the following AEs are to be considered AESI:

- any AE of occurrence of suicidal ideation or behavior, including a positive response to question 1 to 5 of C-SSRS,
- a depression assessed as moderate or worse by the investigator or a score ≥ 15 in the HADS score,
- any grade 3 or higher psychiatric condition, and/or
- any of the following GI TEAEs: vomiting, diarrhea with an increase of at least 4 stools per day over baseline (Grade 2 CTCAE) for at least 3 days.
- any signal that may arise from Sponsors ongoing safety review during the trial that may need closer monitoring.

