  - any AE of occurrence of suicidal ideation or behavior, including a positive response to question 1 to 5 of C-SSRS,
  - a depression assessed as moderate or worse by the investigator or a score ≥ 15 in the HADS score,

- o any grade 3 or higher psychiatric condition, and/or
- any of the following GI TEAEs: vomiting, diarrhea with an increase of at least 4 stools per day over baseline (Grade 2 CTCAE) for at least 3 days.
- Additional wording was added to clarify that AESIs should be reported in the same manner as SAEs.
- Dose modification language was revised to clarify that patients will be permanently discontinued from the study drug in the event that a TEAE meets the discontinuation criteria.
- A typographical error was corrected in the Pregnancy section. The reference to "Inclusion Criterion 9" was changed to "Inclusion Criterion 8".
- Collection of PK samples were updated to collect and generate PK-profiles in patient within the psoriasis indication as follows:
  - PK samples were revised from "trough" to "plasma".
  - The number of optional PK blood samples was increased from "4" to "4 or 5".
  - The date of collection for optional PK samples was revised from Week 8 to Week 16.
  - PK timepoints were revised from "1.5 hours" to "45 minutes" and "4.5 hours" to "4 hours" after intake of the study drug.
  - An additional optional 8-hour blood sample was added.
- Statistical methods and planned analyses were revised as follows:
  - The ITT population was revised to include "all randomized patients who receive at least 1 dose of study drug" as the decision to withdraw patients cannot be biased by knowledge of the assigned treatment due to blinding.
  - Efficacy analysis was revised to remove the condition "using observed cases only" for consistency with the ITT and PP analyses. The only difference in the efficacy analysis should be the number of patients included.
  - The supportive analysis was clarified in the analysis of the primary efficacy endpoint. The sentence "The mixed model for repeated measures may be used as a supportive analysis." was changed to "As a supportive analysis, a mixed model for repeated measures will be performed with treatment group, visit and treatment-by-visit interaction as factors and baseline EASI score by-visit interaction as a covariates".

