- The exclusion criteria no. 14 on absolute neutrophil count and absolute lymphocyte count are by mistake not consistent with the reference range of the central laboratory and was corrected per notification letter dated 09. February 2023, as follows:
  - Absolute neutrophil count of less than 3.0x109 /L (less than 3000/mm3) was corrected to the lower normal range of the Central Laboratory (LNR) i.e. 1.7 x 109 /L (1700/mm3).
  - Absolute lymphocyte count of less than 1.0 x 109 /L (less than 1000/mm3) was corrected to the lower normal range of the Central Laboratory (LNR) i.e. 0,9 x 109 /L (900/mm3).
- The section regarding treatment discontinuation has been updated to more clearly state the requirement that if a patient experiences a TEAE assessed as Grade 3 or higher using the unique clinical descriptions of severity (Grade 2 or higher for the SOC of cardiac disorders) according to CTCAE version 5, the patient should be permanently discontinued from the study drug and not receive additional doses.
- Planned dosing schedule and adjustments has been described in more detail. This to help guide the Investigator in case of temporarily decreasing the dosage regimen if GI or other AEs considered probably or definitely related to the study drug are reported with a severity not compatible with maintaining the treatment as per-protocol.
  - A section for planned dosing schedule Titration over a maximum of 2 weeks has been created.

- A section describing the short dose reduction during the titration period has been updated.
- A section describing dose reductions and temporary treatment discontinuations after the titration period has been created.
- A section describing the examples of supportive treatment for side effects and medical treatment for tolerability issues that may arise during the treatment (e.g. metoclopramide for nausea/vomiting, loperamide for diarrhea, acetaminophen/paracetamol and NASID for headache) have been added.
- Safety blood samples for week 12 have been added in Table 4. Schedule of Assessments, to allow for closer monitoring of all safety laboratory assessments (hematology, serum chemistry, urinalysis) between weeks 8 and 16.
- The adverse events section has been updated with details to emphasize that all AEs must be graded by using the CTCAE grading system version 5.0, with reference to the unique clinical descriptions of severity for each AE in the guidance document.

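### Sections 11.6 and 11.7 let the Investigator restart study drug after a depression or suicidal-ideation event even when that event meets the Section 11.8.1 criterion for permanent discontinuation

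*Protocol*

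**What the plan says.** Protocol Section 11.8.1 requires every adverse event to be graded by CTCAE version 5.0. For a "TEAE assessed as Grade 3 or higher using the unique clinical descriptions of severity" it then states that "the patient should be permanently discontinued from the study drug and not receive additional doses". Its only special case is a stricter threshold, Grade 2 or higher, for cardiac disorders.

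Two other sections give their own dosing pathway for psychiatric events:

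- **Section 11.6 (HADS).** "Patients with a clinically significant worsening of depressive symptoms or new occurrence of clinically significant depression during the study may be referred", the referral being to a mental health specialist. After that evaluation the Investigator, consulting the specialist, decides whether to restart or stop for good.
- **Section 11.7 (C-SSRS).** For a yes to any of questions 1 to 5 after baseline, the patient should be referred and "the study medication should be paused". After the evaluation, "the final decision on restarting or permanently discontinuing study treatment will be at the discretion of the Investigator", again in consultation with the specialist. Section 11.6 uses the same wording for this decision.

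Both sections send the reader only to Section 11.8.2. That section lists "any grade 3 or higher psychiatric condition" among the adverse events of special interest and sets 24-hour reporting, but it contains no dosing rule.

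**The concern.** A patient could have a treatment-emergent depression or ideation event that triggers 11.6 or 11.7 and also meets the 11.8.1 criterion. The site would then hold two instructions that disagree about further dosing. Someone faced with a positive C-SSRS will naturally turn to 11.7, which reads as a complete pathway: refer, pause, evaluate, decide. It calls the Investigator's decision final and does not say that another section may already have settled the matter.

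What is at stake is patient safety and consistency between sites. Section 4.3.2 treats depression and suicidal thoughts as a class risk about which patients must be warned, and it reports one patient on 40 mg in the psoriasis trial with self-injurious behavior without suicidal intent. Two sites could handle the same event differently, each following a section of the protocol.

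**Working it through.** The plan gives no figure to reproduce and the point rests on no statistical calculation. The check sets the sections side by side and counts what each contains.

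| Feature | 11.8.1 | 11.6 | 11.7 |
|---|---|---|---|
| Trigger | CTCAE Grade 3 or higher by the unique clinical descriptions (Grade 2 or higher for cardiac disorders) | Clinically significant new or worsening depression | Yes to any of C-SSRS questions 1 to 5 |
| Severity limit on restart | Restart not allowed | None | None |
| Pause stated | Permanent stop | No | Yes |
| Referral | Not addressed | Optional | Should be made |
| Who decides on restart | Nobody; no discretion given | Investigator with specialist | Investigator with specialist |
| Refers to 11.8.1 | n/a | No | No |
| Refers to 11.8.2 | n/a | Yes | Yes |

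1. *Does either pathway stop short of the 11.8.1 criterion?* No. Of the two sections that allow a restart, 0 of 2 set a grade limit and 0 of 2 refer to 11.8.1.

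2. *Is there a precedence rule elsewhere?* Sections 7.4 and 8.3 to 8.3.3 contain none, and no sentence in the protocol or SAP says which section governs.

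3. *Can the overlap occur?* Section 11.8.2 expects psychiatric conditions of Grade 3 or higher. The documents do not show which psychiatric terms meet 11.8.1. Table 6 names 6 terms (diarrhea, nausea, vomiting, headache, raised ALT, raised AST), of which 0 are psychiatric, and sends the reader to the full CTCAE for the rest. The triggers in 11.6 and 11.7 are not CTCAE grades, so many triggered cases may fall below the criterion.

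4. *Where do the rules part?* Permanent discontinuation satisfies all three sections. The conflict therefore arises only if the Investigator restarts an event that meets 11.8.1. Below that criterion the discretion stands and nothing is inconsistent.

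5. *Is a restart practically possible?* In Table 4, HADS and C-SSRS are scheduled at 6 post-baseline visits: Weeks 2, 4, 8, 12, 16 and 20. Study drug is dispensed at 4 of those 6: Weeks 2, 4, 8 and 12. An event found at any of those four leaves planned dosing ahead. This describes opportunity, not frequency.

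**The case against.** The strongest reply is that the sections can be read together. Section 11.8.1 covers every treatment-emergent event that meets its criterion. Sections 11.6 and 11.7 offer a choice between restarting and stopping, and 11.8.1 simply removes the first option when it applies. Their low triggers, which include a wish to be dead, leave the discretion useful for milder events. On this view only a cross-reference is missing.

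The amendment summary in Appendix 15 supports that as the sponsor's intent. Amendment 1 clarified that "patients will be permanently discontinued from the study drug in the event that a TEAE meets the discontinuation criteria", and Amendment 2 describes the section as "updated to more clearly state the requirement that if a patient experiences a TEAE assessed as Grade 3 or higher".

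There are also safeguards: the pause in 11.7, specialist consultation, and 24-hour reporting. Section 7.4 allows withdrawal of a patient whose condition no longer fits the eligibility criteria, which include a yes to C-SSRS question 4 or 5 and, subject to the Investigator's opinion, major depression with a HADS depression score of 15 or more. Finally, the overlap is conditional. The 11.8.2 item does not mention the unique clinical descriptions, so it could include events graded by the general guidance in Table 7, which 11.8.1 does not clearly cover.

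Much of this stands. The intended answer is fairly clear, the safeguards narrow the gap, and the frequency is unknown. But the combined reading has to be inferred, against a more specific section that calls the Investigator's decision final. The amendment summary shows intent without putting it into 11.6 or 11.7. The withdrawal route in 7.4 is permissive, and none of the safeguards bars a restart. Section 11.6 does not state even a pause.

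**Conclusion.** The concern holds. For a depression or suicidal-ideation event that meets the 11.8.1 criterion, the protocol as written gives two different answers on re-dosing and does not rank them.

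The conclusion is conditional on the event meeting that criterion; the CTCAE itself is needed to say which psychiatric terms do. Section 11.8.1 is worded as what should happen, so this is an unreconciled instruction rather than an express permission to override the stop. The number of affected patients cannot be estimated from the documents, and no rate is assumed. Sample size, power and type I error are unaffected. The point should be corrected because it concerns dosing after an event that the protocol itself names as a class risk, and the correction is small.

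**What to change.** Add to both 11.6 and 11.7, next to the sentence on the restart decision: *Study treatment may be restarted after specialist evaluation only if the event does not meet the permanent-discontinuation criterion in Section 11.8.1.* Do not repeat the grade there, so that the wording of 11.8.1, including its reliance on the unique clinical descriptions, remains the single source.

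The cost is one sentence in each of two sections and the loss of Investigator discretion in what are probably few cases. Because the change concerns dosing after a safety event, it may be classed as substantial under Section 15.7.1 and need approval before use; it could be combined with the next amendment. Planned data collection does not change: under Section 8.3 a patient who stops permanently stays in the study for safety evaluation.

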# Table 6. Selected unique clinical descriptions of severity of AEs from National CancerInstitute Common Terminology Criteria for Adverse Events version 5.0

Headache	Mild pain	Moderate pain; limiting instrumental ADL	Severe pain; limiting self care ADL	-	-
Alanine aminotransferase increased	>ULN - 3.0 x ULN if baseline was normal; 1.5 - 3.0 x baseline if baseline was abnormal	>3.0 - 5.0 x ULN if baseline was normal; >3.0 - 5.0 x baseline if baseline was abnormal	>5.0 - 20.0 x ULN if baseline was normal; >5.0 - 20.0 x baseline if baseline was abnormal	>20.0 x ULN if baseline was normal; >20.0 x baseline if baseline was abnormal	-
Aspartate aminotransferase increased	>ULN - 3.0 x ULN if baseline was normal; 1.5 - 3.0 x baseline if baseline was abnormal	>3.0 - 5.0 x ULN if baseline was normal; >3.0 - 5.0 x baseline if baseline was abnormal	>5.0 - 20.0 x ULN if baseline was normal; >5.0 - 20.0 x baseline if baseline was abnormal	>20.0 x ULN if baseline was normal; >20.0 x baseline if baseline was abnormal	-
Other AEs	For other AEs not reference to the un uniquely describe classification is to	in this table, please nique clinical descri d in the CTCAE gra be used.	e refer to the CTCA iptions of severity for ading system, the ge	E grading system vertex or each AE. Only if eneral guidance (see	ersion 5.0, with an AE is not Table 7) for

# Table 7. National Cancer Institute Common Terminology Criteria for Adverse Eventsgeneral guideline for classification version 5.0

**GRADE 1:** Mild: asymptomatic or mild symptoms; clinical or diagnostic observations only; intervention not indicated.

**GRADE 2:** Moderate: minimal, local, or noninvasive intervention indicated; limiting age-appropriate instrumental ADL.

**GRADE 3:** Severe or medically significant but not immediately life threatening; hospitalization or prolongation of hospitalization indicated; disabling; limiting self-care ADL.

**GRADE 4:** Life threatening consequences; urgent intervention indicated.

**GRADE 5:** Death related to an AE.

Abbreviations: ADL, activities of daily living; AE, adverse event.

#### Table 8. Classification of Adverse Events by Relationship to Study Drug

**UNRELATED:** This category applies to those AEs that are clearly and incontrovertibly due to extraneous causes (disease, environment, etc).

**UNLIKELY:** This category applies to those AEs that are judged to be unrelated to the test drug but for which no extraneous cause may be found. An AE may be considered unlikely to be related to study drug if or when it meets 2 of the following criteria: (1) it does not follow a reasonable temporal sequence from administration of the test drug; (2) it could readily have been produced by the patient's clinical state, environmental or toxic factors, or other modes of therapy administered to the patient; (3) it does not follow a known pattern of response to the test drug; or (4) it does not reappear or worsen when the drug is readministered.

**POSSIBLY:** This category applies to those AEs for which a connection with the test drug administration appears unlikely but cannot be ruled out with certainty. An AE may be considered possibly related if or when it meets 2 of the following criteria: (1) it follows a reasonable temporal sequence from administration of the drug; (2) it could not readily have been produced by the patients' clinical state, environmental or toxic factors, or other modes of therapy administered to the patient; or (3) it follows a known pattern of response to the test drug.

**PROBABLY:** This category applies to those AEs that the Investigator feels with a high degree of certainty are related to the test drug. An AE may be considered probably related if or when it meets 3 of the following criteria: (1) it follows a reasonable temporal sequence from administration of the drug; (2) it could not be reasonably explained by the known characteristics of the patients' clinical state, environmental or toxic factors, or other modes of therapy administered to the patient; (3) it disappears or decreases on cessation or reduction in dose (note that there are exceptions when an AE does not disappear upon discontinuation of the drug, yet drug-relatedness clearly exists; for example, as in bone marrow depression, fixed drug eruptions, or tardive dyskinesia); or (4) it follows a known pattern of response to the test drug.

**DEFINITELY:** This category applies to those AEs that the Investigator feels are incontrovertibly related to test drug. An AE may be assigned an attribution of definitely related if or when it meets all of the following criteria: (1) it follows a reasonable temporal sequence from administration of the drug; (2) it could not be reasonably explained by the known characteristics of the patients' clinical state, environmental or toxic factors, or other modes of therapy administered to the patient; (3) it disappears or decreases on cessation or reduction in dose and recurs with re-exposure to drug (if rechallenge occurs); and (4) it follows a known pattern of response to the test drug.

Abbreviation: AE, adverse event.

# **11.8.2** Adverse Events of Special Interest (AESI)

An AESI (serious or nonserious) is one of scientific and medical concern, for which ongoing monitoring and rapid communication by the Investigator to the Sponsor could be appropriate. AESIs must be reported within 24 hours of occurrence or when the Investigator becomes aware of the event, following SAE reporting procedures (Section 11.8.4). Such an event might require further investigation to characterize and understand it. Depending on the nature of the event, rapid communication by the trial Sponsor to other parties (eg, regulators) might also be warranted.

In this trial, the following AEs are to be considered AESI:

- any AE of occurrence of suicidal ideation or behavior, including a positive response to question 1 to 5 of C-SSRS,
- a depression assessed as moderate or worse by the investigator or a score ≥ 15 in the HADS score,
- any grade 3 or higher psychiatric condition, and/or
- any of the following GI TEAEs: vomiting, diarrhea with an increase of at least 4 stools per day over baseline (Grade 2 CTCAE) for at least 3 days.
- any signal that may arise from Sponsors ongoing safety review during the trial that may need closer monitoring.

